- Planned minimum follow up of 24 months
- Recruitment period: November 1, 2015 to October 31, 2018

August 12, 2016

- Total sample size
 - o CFLD NET: 224 subjects currently followed in CFLD NET
 - 128 normal US pattern
 - 22 homogeneous US pattern
 - 39 heterogeneous US pattern
 - 35 cirrhosis US pattern

Transient elastography is currently available at 8 centers. So current potential eligible subject numbers are shown in the table below:

	Total Subjects	NL	HMG	HTG	CIR
Centers with TE	166	90	19	33	24
3 Centers without TE	58	38	3	6	11
Total possible	224	128	22	39	35

Number of clinical centers: 8 (could expand to the full 11 based on Fibroscan availability). Washington University has the most subjects in longitudinal followup who will not be in this substudy initially (30 (21 NL, 4 HTG, 2 HMG, 3 CIR)

Visit schedule:

- TE with annual laboratory visit

Background and Goals

Noninvasive monitoring of liver fibrosis is an unmet critical need in CF liver disease. Liver biopsy is infrequently used in CF due to the patchy nature of liver involvement and is not suitable for longitudinal studies of progressive liver disease in CF. Indeed, unlike many other liver diseases, synthetic dysfunction is rare in CF liver disease. Portal hypertension due to hepatic fibrosis mediates most if not all of the complications seen in CF liver disease.

Liver involvement in CF is common, but progression to advanced liver disease (cirrhosis with portal hypertension) occurs in only 5-7% of individuals with CF. The mean age of diagnosis of advanced liver disease in CF is between 10 and 15 years of age suggesting that this is a disease of childhood. We have been conducting a prospective longitudinal cohort study to determine the utility of grayscale liver ultrasound pattern to predict the development of advanced liver disease in children with CF (PUSH: Clinical Trials: NCT01144507) for 5 years. Preliminary studies in children with CF have suggested that TE can identify children with advanced liver disease (1-4). However, to our knowledge, there has not been a prospective study of longitudinal changes in elastography in children with CF nor studies of the predictive utility of elastography for complications of liver disease in children and young adults with CF and liver disease. The addition of elastography to the ongoing PUSH study in the CFLD NET provides a unique opportunity to evaluate the

August 12, 2016

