- Hypothesis 4b: Higher fat content will be associated with a lower risk of progression to a nodular pattern on US
-
- Aim 5: To determine if TE can predict the development of portal hypertension and its complications in children and young adults with CF and a nodular pattern on US.
 - Hypothesis 5: Among those children with a nodular pattern on US, TE results will correlate with clinical findings of portal hypertension (splenomegaly, thrombocytopenia, variceal hemorrhage and/or ascites)
- Aim 6: To pilot the correlation of TE and hepatic fibrosis and fat content in children and young adults with CF who have a clinically indicated liver biopsy.
 - Hypothesis 6: TE assessment of liver stiffness and fat content will correlate with steatosis and fibrosis staging on liver biopsy in CF

Inclusion/Exclusion Criteria

Inclusion criteria:

- Participants enrolled in CFLD NET PUSH study in longitudinal follow up at centers with Fibroscan available (currently 8/11 centers)
- Entry criteria for that study were:
 - CF as determined by sweat chloride >60 meq/l
 - Pancreatic insufficiency
 - Age 3-12 years old at entry
 - For entry into the longitudinal follow up subjects were in one of two groups
 - A screening US pattern of nodular liver (CIR), heterogeneous increased echogenicity (HTG) or homogeneous increased echogenicity (HMG)
 - A screening US pattern of normal (NL) matched to a HTG subject (2 NL:1HTG) by age, center and pseudomonas status

Exclusion criteria:

- Exited from the PUSH Study
- Unable / unwilling to sign consent

Recruitment, enrollment and follow-up

- Planned minimum follow up 2 years
- Recruitment period: November 1, 2016 to October 31, 2019
- Total sample size 200 subjects assuming a 90% success

US pattern	Subjects in Study at	Potentially available
------------	----------------------	-----------------------

August 12, 2016

	centers with TE	subjects at centers currently without TE
NL	90	38
HTG	33	6
HMG	19	3
CIR	24	11

Study Procedures

The research protocol will encompass the prospective longitudinal analysis of FibroScan measurements of liver stiffness in children with CF who are enrolled in the PUSH study. Visits will occur annually for at least two years, therefore there will be a minimum of three assessments, a baseline and at least two annual follow up visits.

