- “Controlled Attenuation Parameter (CAP)” quantifies liver steatosis and is measured in dB/m (median of 10 subsequent valid measurements).

In addition quality control data are collected:

- Invalid measurements and success rate
- Number and list of valid measurements
- Inter quartile range (IQR) (kPa or dB/m) of all valid measurements within the examination (reflects the dispersion of stiffness or CAP measurements)
- IQR/med. (%) Indicates the IQR/median ratio and should remain as low as possible to ensure reliable results (goal < 30%)

Study withdrawal/discontinuation

The participant and/or participant’s family may withdraw from the study at any time. The study investigator can withdraw the participant from the study at any time if that is felt to be in the best interest of the participant and/or their family. If a participant in the longitudinal follow up study meets an endpoint for the end of the PUSH study (liver transplantation or death) they will have met the end of this study.

Statistical and Design Considerations

Based upon interest and involvement of the subjects in PUSH, we anticipate all subjects currently available (168) will enroll. If TE becomes available at the 3 centers without TE, then up to an additional 60 subjects would be available to enroll. TE would be available from all eligible US pattern subjects.

Hypothesis 1: TE results can differentiate children with a heterogeneous or homogeneous pattern on grayscale liver US who will progress to a nodular pattern on US

Analysis:

To test whether TE, when combined with US pattern characterization can improve the prediction of progression to a nodular pattern on US, we will build two discrete survival models using logistic regression. In the first model, greyscale US consensus grade will be used to predict prediction to nodular pattern. In the second model, we will add the predictor liver stiffness measured by TE. If the second model significantly increases the area under the receiver operating characteristic curve

August 12, 2016

(AUROC) comparing to the first model, we will conclude that TE can improve the prediction of progression to a nodular pattern on US. All subjects graded as NL, HMG, or HTG at the time this ancillary study starts will be included in the analysis.

Power calculations:

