The estimated 2-4 year progression rate is ~40% in HTG subjects. Thus of the 33 available with HTG pattern, 10-13 would be predicted to progress to CIR. However, as the study is in progress, ~20% have progressed so the risk of progression may be lower. We choose to make a conservative assumption in our power calculation: 20% of HTG subjects will progress to CIR pattern, and 2% of NL or HMG subjects will progress to CIR pattern. In addition, we assume the liver stiffness measure follow a lognormal distribution with location =0 and scale parameter =0.5 (i.e. median=1, Q1=0.71, Q2=1.4). With 142 subjects (approximately 63% NLs, 23% HTGs, and 13% HMGs) we will have 80% power to detect an odds ratio of 4 for a 1 unit increase in the liver stiffness measure. (Caveat: Given that we do not have any preliminary data of TE measures in CF subjects, the results of this power calculation only give us a general guidance).

Hypothesis 2a: Valid TE measurements will be obtained in more than 90% of children with CF

Analysis:

For hypothesis 2a, we will estimate the proportion of subjects in whom a valid transient elastography measurement can be obtained. At each site, all measurements will be performed by one of the trained examiners. The results will be reported as the median of 10 valid measurements and will be accepted as valid if the ratio of the interquartile range (IQR) and median was < 30% and the success rate was > 60% (8, 9). Per Goldschmidt 2013 (9) we will define two measures of the feasibility of transient in our population: “technically possible” and “acceptable quality.” The proportion of subjects with a “technically possible” FibroScan™ is defined as the number of subjects with at least 10 FibroScan™ measurements obtained divided by the number assessed. The proportion of subjects with FibroScans™ of “acceptable quality” is defined as the number of subjects with FibroScan™s with the ratio of the interquartile range and median of the 10 measurements <30%, divided by the number assessed. The proportions and their 95% confidence intervals will be provided using the Wald method. We will do a stratified (separate) analysis by <8 years of age and >8 years of age. There will be the opportunity to compare this data to children with other liver diseases in the ChiLDReN FORCE study.

Hypothesis 2b: To determine the variability of TE measurements taken at different liver sites in the same patient

Analysis

August 12, 2016

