For this analysis we will include all subjects with a nodular US pattern (CIR). The primary outcome will be a composite outcome defined as occurrence of any of the following three endpoints:

August 12, 2016

Hypersplenism: platelets <150,000
Variceal hemorrhage
Splenomegaly as indicated by a palpable spleen
Ascites as clinically detected ascites

A discrete survival analysis using logistic regression will be used to test whether transient elastography results are associated with risk of developing liver cirrhosis complications. The predictor will be most recent TE results.

Power calculation:

Previous literature has reported mean a rate of variceal hemorrhage between 5 and 10% per year with CF and cirrhosis. There is no data for rates of development of splenomegaly or thrombocytopenia in CF with a nodular US pattern. With currently 33 subjects with a nodular US pattern and 90% successful rate of TE, we anticipate 3 to 6 subjects (10% ~20%) among 30 subjects developing one of the endpoints in 2 years. We assume the true difference in population mean TE measurements is 19 kPa between subjects with and without portal hypertension; we assume the SD is 22.0 kPa and 6.0 kPa for subjects with and without portal hypertension, respectively. Our calculation shows that using 2-sided likelihood ratio Chi-square test (Type I error rate 5%) there will be 80% power to detect odds ratio 4 ~ 5 per 10kPa increase in TE results.

Hypothesis 6: TE assessment of liver stiffness and fat content will correlate with steatosis and fibrosis staging on liver biopsy in CF

Analysis: ANOVA or Kruscal-Wallis test, whichever is appropriate, will be used to compare TE measures between groups based on steatosis and fibrosis staging on liver biopsy in CF.

Human research participant issues

Institutional Review Board Approval

Local institutional review board approval will be obtained for the study. IRB approvals will be centrally collated at the Data Coordinating Center.

Standard of Care

Standards of care for the management of liver disease at each of the CFLD NET sites will be followed. At present there are no clinical standards for interventions based on TE-measured liver stiffness for pediatric CF patients and thus there are no expected interventions based solely on TE measurements.

Consent

Informed consent and assent (when appropriate according to local standards) will be obtained prior to any research activities. A common template for

August 12, 2016

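### The Hypothesis 5 power calculation starts from 33 nodular subjects, but the protocol's own tables give 24 at the centers that now have TE, so the 30 evaluable subjects, 3 to 6 events and 80% power do not hold on the current basis.

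*Protocol*

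**What the plan says.** In the Protocol, Statistical and Design Considerations, the power calculation under Hypothesis 5 states "With currently 33 subjects with a nodular US pattern and 90% successful rate of TE, we anticipate 3 to 6 subjects". It puts the evaluable set at 30 and the two-year event rate at 10-20%. It assumes a 19 kPa difference in mean TE, with SDs of 22.0 kPa with portal hypertension and 6.0 kPa without. From a two-sided 5% likelihood ratio chi-square test it claims 80% power for an odds ratio of 4 to 5 per 10 kPa.

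The counts elsewhere in the Protocol are:

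- Design Synopsis table, columns total, NL, HMG, HTG, CIR: "Centers with TE 166 90 19 33 24". The nodular count is the last column, 24.
- Design Synopsis, whole network: "35 cirrhosis US pattern".
- Table under Recruitment, enrollment and follow-up: CIR 24 at centers with TE and 11 at centers currently without it; HTG 33 at centers with TE.
- Hypothesis 1 power text: "Thus of the 33 available with HTG pattern, 10-13 would be predicted to progress to CIR".

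On the remaining three centers, the synopsis says the study "could expand to the full 11 based on Fibroscan availability".

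**The concern.** The Hypothesis 5 paragraph describes its 33 nodular subjects as current. Currently, TE exists at 8 centers, and both tables put 24 nodular subjects there. The figure 33 does appear in both tables, but as the HTG count at TE centers.

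The number is not a stray misprint, because the rest of the paragraph follows from it: the 30 evaluable subjects, the 3 to 6 events and the 80% power. If the input is too high, a reader of Aim 5 will expect more information than the participating centers can supply. The true number of events may be so small that a logistic model can barely be fitted.

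**Working it through.** **Inputs.** From the Hypothesis 5 paragraph: 33 subjects, 90% TE success, 10-20% events in two years, 19 kPa difference, SDs 22.0 and 6.0 kPa, two-sided 5% likelihood ratio test, odds ratio 4-5 per 10 kPa. From the tables: CIR 24 (TE centers), 11 (others), 35 (all).

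**1. Reproduce the protocol's counts.** 33 × 0.90 = 29.7, about 30. 10% and 20% of 30 are 3 and 6. The arithmetic is sound given 33.

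**2. Reproduce the protocol's power.** Model: logistic regression on one normal covariate, with power taken from a noncentral chi-square with 1 df. The noncentrality is λ = 2n × (expected log-likelihood per subject under the full model minus that under the null model). The protocol gives no overall covariate SD, so one is assumed here, the SD of the two-group mixture at 10% events:

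√(0.1 × 22² + 0.9 × 6² + 0.1 × 0.9 × 19²) = √(48.4 + 32.4 + 32.5) = 10.64 kPa.

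The event probability at the mean covariate is set to 10% or 20%, also an assumption. These settings were chosen because they recover the stated result.

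| n | Power, 10% events, OR 5 | Power, 20% events, OR 4 | OR at 80% power (10%; 20%) |
|---|---|---|---|
| 30 (from 33) | 0.802 | 0.811 | 4.98; 3.90 |
| 22 (from 24) | 0.672 | 0.682 | 7.14; 5.45 |
| 32 (from 35) | 0.826 | 0.835 | 4.68; 3.68 |

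The first row matches the stated 80% and odds ratio 4-5.

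**3. Put in the tabulated count.** 24 × 0.90 = 21.6, about 22. 10-20% of 21.6 is 2.2 to 4.3, so about 2 to 4 events. Power is about 67-68% (second row).

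**4. Hand check.** λ is proportional to n. Power of 80% at two-sided 5% needs λ = (1.960 + 0.842)² = 7.85. Moving from 30 to 22 gives 7.85 × 22/30 = 5.76, whose square root is 2.40. Power is then Φ(2.40 − 1.96) = Φ(0.44) = 0.67. So if the stated 80% at n=30 is accepted, the drop to about 67% follows in this framework.

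**5. Sensitivity.** Absolute power depends on the unstated SD and on how the event rate enters.

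| Setting | n=30 | n=22 |
|---|---|---|
| SD 13.54 kPa (mixture at 20% events), 20% at the mean, OR 4 | 0.919 | 0.819 |
| SD 13.54 kPa, 20% as the marginal rate, OR 4 | 0.860 | 0.741 |
| SD 10.64 kPa, 10% at the mean, OR 4 | 0.696 | 0.563 |
| SD 10.64 kPa, 10% as the marginal rate, OR 4 | 0.544 | 0.426 |

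The variants that leave n=22 near or above 80% start well above 80% at n=30, so they are not the calculation that the protocol reports.

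**6. Look for another source of 33.** The whole network gives 35. The statistics section's own total, "we anticipate all subjects currently available (168) will enroll", less the 142 non-nodular subjects of Hypothesis 1 (90 + 33 + 19) leaves 26. Neither is 33.

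**The case against.** **33 may be a network figure.** It is close to 35, and the statistics section's counts already differ slightly from the tables (168 against 166, and 60 against 58). The recruitment section states "Total sample size 200 subjects assuming a 90% success", and 224 × 0.9 = 201.6 points to a network-wide basis there. On that reading the fault is an unstated condition rather than a wrong row. This cannot be excluded. But the paragraph says the subjects are current, and Hypothesis 1 counts TE-center subjects only (142). A reader might infer that 33 was copied from the HTG column. The numerical match is a fact, but the copying is only an inference.

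**More nodular subjects may come.** A reader might infer that the subjects simply cannot be had. The documents do not support that. If all three remaining centers obtain TE, 35 × 0.9 = 31.5 evaluable subjects meet the stated power. The analysis set is also not restricted to grade at study start. On the protocol's own progression rates, 24 + 0.20 × 33 + 0.02 × 109 = 32.8 subjects would be nodular at some time. Two years is a minimum, so later events may also count. These points stand, but they concern conditional or future cases, the latter with shorter follow-up. They do not make the current count 33.

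**The aim is exploratory.** It sets no recruitment target, since everyone available is to be enrolled, and the 142 for the primary aim is unaffected. The corrected 2-4 events overlap the stated 3-6. This stands and limits the severity.

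**Conclusion.** The mismatch holds: the protocol's current nodular count at TE centers is 24, and the power paragraph uses 33. On the current basis Aim 5 has about 22 evaluable subjects and about 2 to 4 events. Power is about 67-68% where 80% is claimed, or the detectable odds ratio is about 5.5-7 per 10 kPa rather than 4-5.

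These power figures rest on an assumed covariate SD of about 10.6 kPa and an event probability of 10-20% at the mean covariate. At 20% events with an SD of 13.5 kPa, n=22 still gives about 0.74-0.82 for an odds ratio of 4. It would therefore be wrong to treat any single replacement power as established by the documents. With 2 to 4 events the large-sample chi-square approximation is itself weak.

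This should be fixed because a numerical power claim is made and does not follow from the protocol's own counts. It is not a defect of the primary aim.

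**What to change.** In the Hypothesis 5 power paragraph, replace 33, 30 and 3-6 with 24, about 22 and about 2-4, and say that the basis is the 8 centers with TE. Then do one of two things:

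- Rerun the calculation and restate the power or the detectable odds ratio, showing the covariate SD, the event rate and how each enters.
- Drop the power claim and label Aim 5 descriptive.

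If the 11-center case is wanted, add it as a separate line (35 subjects, about 32 evaluable), explicitly conditional on TE becoming available at the other three centers. If 33 had some other source, state it and reconcile it with the tables.

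The cost is one corrected paragraph and a short recalculation by the trial statistician. Design, procedures and enrollment do not change. The stated power will probably look less favourable.

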Variability of TE measurements at a single liver site will be quantified by the ratio of the interquartile range and the median (RIM). Absolute difference in RIM between the two liver measuring sites in the same patient will be calculated. Distribution of this absolute difference will be studied using kernel density estimation to identify whether the distribution has more than one mode (whether these are heterogeneous groups according to difference in variabilities between sites in the same patient). We will also study whether this RIM is associated with the median of the stiffness measurements in the same patient.

Hypothesis 3: TE based values will correlate with conventional biomarkers of fibrosis/liver disease severity in CF: APRI, Fib-4, platelet count and spleen size

Analysis: Graphic method will be used to explore relationship between TE based values and conventional biomarkers. Pearson or Spearman correlation will be calculated.

Exploratory analyses:

Hypothesis 4a: The combination of grayscale liver US image pattern assessment and TE values with fat content will differentiate between those individuals with dichotomous radiology grades (2HTG/2NL 2HTG/2HMG or 2HTG/2CIR) and risk of progression to cirrhosis.

Analysis:

ANOVA or Kruskal-Wallis test, whichever is appropriate, will be used to compare TE measures between the three groups.

Hypothesis 4b: Higher fat content will be associated with a lower risk of progression to cirrhosis

To test whether subjects with a high TE determination of fat content and heterogeneous pattern on US will not progress to an US pattern of cirrhosis (Hypothesis 5b), we will add the TE measure of fat content to the second model for testing hypothesis 1 (i.e. this model will include three predictors: grayscale US, liver stiffness, and fat content). The hypothesis can be tested through testing the regression coefficient for the fat content variable. A significant negative regression coefficient will support our hypothesis. All subjects graded as NL, HMG, or HTG at the time this ancillary study starts will be included in the analysis.

Hypothesis 5: Among those children with a nodular pattern on US, TE results will correlate with clinical findings of portal hypertension (splenomegaly, thrombocytopenia, variceal hemorrhage and/or ascites)

Analysis:

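### Hypothesis 6 is about correlation with ordered biopsy stages, but the planned ANOVA or Kruskal-Wallis test ignores the order and gives no correlation estimate

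*Protocol*

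**What the plan says.** Under Study Aims and Hypotheses, the protocol's sixth aim is "To pilot the correlation of TE and hepatic fibrosis and fat content" in participants who have a biopsy for clinical reasons. Hypothesis 6, repeated under Statistical and Design Considerations, is that "TE assessment of liver stiffness and fat content will correlate with steatosis and fibrosis staging on liver biopsy in CF".

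The analysis given there is one sentence: ANOVA or Kruskal-Wallis, depending on which suits the data, "will be used to compare TE measures between groups based on steatosis and fibrosis staging on liver biopsy in CF". No correlation coefficient, trend test or confidence interval is named. It is also not said which TE measure goes with which biopsy scale.

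For Hypothesis 3, which uses the same verb for laboratory and clinical markers, the protocol says "Pearson or Spearman correlation will be calculated".

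The number of biopsies, the staging scale and the number of categories are not given. Background and Goals says that "Liver biopsy is infrequently used in CF due to the patchy nature of liver involvement", so few are to be expected.

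**The concern.** Fibrosis stage and steatosis grade are ordered. A claim that TE correlates with them is a claim about movement along that order. ANOVA and Kruskal-Wallis give the same answer if the stage labels are shuffled, so a significant result could come from any pattern of differences, including one that rises and then falls. A pilot is mainly worth its estimate, and these tests do not supply the estimate the aim names.

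The omnibus test also spreads its power over k − 1 degrees of freedom for k stages, where a trend test uses one. In a small sample that can matter.

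This is not a detail left to a statistical analysis plan. The protocol fixes a method, and the method does not match the stated aim.

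**Working it through.** **No figure to reproduce.** Hypothesis 6 has no sample size, effect size or power statement.

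**1. What each test uses.** Let r_s be the Spearman correlation of TE with stage, and η² the between-group share of the sum of squares of the TE ranks.

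- Kruskal-Wallis: H = (n − 1)·η², referred to chi-square with k − 1 degrees of freedom. Stage order does not enter.
- Spearman: uses r_s, where r_s² ≤ η². One degree of freedom, and order does enter.
- With k = 2, η² = r_s², so the two tests carry the same information.

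**2. Large-sample cost of ignoring order.** Assume an exactly linear trend and a two-sided 5% level (not stated for Hypothesis 6; taken from the Hypothesis 5 power calculation). A 1-df test with 80% power has noncentrality (1.960 + 0.842)² = 7.85. Putting 7.85 into a noncentral chi-square with k − 1 degrees of freedom:

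| Groups | df | Omnibus power | N ratio to regain 80% |
|---|---|---|---|
| 3 | 2 | 71% | 1.23 |
| 4 | 3 | 65% | 1.39 |
| 5 | 4 | 60% | 1.52 |

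**3. Small-sample simulation.** Assumptions: bivariate normal latent stage and TE; latent stage cut into equally frequent groups; n = 20; two-sided 5%; standard p-values (F, chi-square, t approximation for Spearman); 20,000 runs per cell, so the Monte Carlo standard error is at most √(0.25/20,000) = 0.35 points. Power in %:

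| Groups | Latent correlation | Kruskal-Wallis | ANOVA | Spearman | Spearman − ANOVA |
|---|---|---|---|---|---|
| 5 | 0.5 | 21.6 | 32.5 | 54.7 | 22.2 |
| 5 | 0.6 | 38.0 | 51.5 | 75.3 | 23.8 |
| 5 | 0.7 | 60.0 | 74.3 | 90.9 | 16.6 |
| 3 | 0.5 | 34.9 | 40.4 | 50.5 | 10.1 |
| 3 | 0.6 | 53.7 | 60.1 | 70.3 | 10.2 |
| 3 | 0.7 | 75.0 | 80.7 | 87.1 | 6.4 |

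With two groups at n = 20, Spearman and Kruskal-Wallis differ by less than 2 points (for example 42.1 against 40.3 at correlation 0.5). That remainder comes only from the p-value approximations; with permutation p-values the two coincide.

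Under no association at n = 20 with five stages, the rejection rates are 2.7% (Kruskal-Wallis), 4.9% (ANOVA) and 5.2% (Spearman). ANOVA is therefore the fairer comparator for the cost of ignoring order.

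**4. Where the gain shrinks or reverses.** Five equal stages, normal errors, 1,500 runs:

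- Only the top stage differs, by 1.5 SD: ANOVA 41% against Spearman 34% at n = 20, and 62% against 48% at n = 30.
- Rise then fall (means 0, 1, 1.5, 1, 0 SD), n = 20: ANOVA 42% against Spearman 8%.

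**The case against.** The strongest reply is that Aim 6 is an exploratory pilot with no power claim and no decision rule. A comparison of TE across stages is a valid test of association, and a correlation could be added later from the same data. All of that stands. It limits the severity but does not remove the mismatch between aim and method.

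The size also depends on choices the protocol leaves open. Its wording allows collapsed stages, which would be natural with few biopsies. With three groups the loss is modest and with two it vanishes. That stands too.

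Three stronger readings are tempting and not supported:

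- *That the planned test has almost no power in a very small pilot.* With 10 biopsies and five stages, a standard Kruskal-Wallis p-value gives only 1–3% power. This mainly reflects the chi-square approximation with about two subjects per group, where its type I error is about 0.2%. A permutation version, which the protocol's wording permits, has 14–28% against 26–54% for permutation Spearman. A gap of about a factor of two remains.
- *That the pilot will probably miss a real association, and that the change would rescue it.* With 30 biopsies, five stages and correlation 0.7, ANOVA has about 94% and Spearman 98%. With 10 biopsies and correlation 0.5, Spearman itself has only about 27%.
- *That the change has no downside if the relation is monotone.* A jump at the top stage alone is monotone, and there ANOVA does better.

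The protocol also says only that TE correlates with staging, not that it rises. An increasing relation is a reasonable inference from its description of stiffness as a measure of fibrosis and CAP as a measure of steatosis.

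**Conclusion.** The point holds in a limited form. The mismatch needs no assumptions: the aim and hypothesis name a correlation, the fixed analysis neither uses stage order nor estimates a correlation, and the protocol handles Hypothesis 3 differently.

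The power loss is conditional on TE changing steadily with stage. At an assumed 20 biopsies and latent correlation of 0.5 to 0.7, ANOVA loses about 20 points to Spearman with five equally frequent stages (17 to 24, depending on the correlation) and 6 to 10 points with three groups. Against Kruskal-Wallis there is no real loss with two groups. The numbers of biopsies and stages and the strength of the relation are all assumptions, because the protocol states none of them.

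Severity is minor. The aim is exploratory, and no primary or secondary conclusion depends on it.

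**What to change.** In Statistical and Design Considerations, Hypothesis 6, replace the analysis sentence so that:

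- the main analysis is a Spearman or Kendall correlation with a 95% confidence interval (for example by bootstrap), or a Jonckheere-Terpstra test if only a trend test is wanted;
- liver stiffness is paired with fibrosis stage, and CAP with steatosis grade;
- ANOVA or Kruskal-Wallis and by-stage plots stay as secondary description, which covers a jump at the top stage or a non-monotone pattern.

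The change is one or two sentences and needs no new data. Its price is somewhat less power than ANOVA if only the highest stage differs, and very little power if the relation is not monotone.

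The estimate will still be imprecise. As a rough guide, with 20 biopsies and an estimated correlation of 0.6, Fisher's transformation gives 0.693 ± 1.96/√17 = 0.218 to 1.168, which is an interval of about 0.2 to 0.8 on the correlation scale. That is still the quantity the pilot sets out to provide.
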